7.6.2 Reporting of ECIs

Overdose and liver toxicity ECIs whether or not related to the Pembrolizumab, occurring from the first dose until 12 weeks following the last treatment dose, or the initiation of a new anticancer therapy, whichever is earlier, must be recorded on the AE e-case report forms and reported using the SAE/ECI report form within 24 hrs of the PI/designee becoming aware of the event to the RM-CTU by [contact] or e-mail [contact] who will in turn notify who will inform the Sponsor and MSD.

7.7 Definition of an Overdose for This Protocol and Reporting of Overdose

At present no specific information is available on the treatment of overdose of pembrolizumab. For purposes of this trial, an overdose will be defined as any dose exceeding the prescribed dose for pembrolizumab by 20%. In the event of overdose, the patient should be observed closely for signs of toxicity. Appropriate supportive treatment should be provided if clinically indicated.

If an adverse event(s) is associated with (“results from”) the overdose of pembrolizumab, the adverse event(s) should be recorded on the AE CRF and reported as a serious adverse event, even if no other seriousness criteria are met.

If an overdose is taken without any associated clinical symptoms or abnormal laboratory results, the overdose is again recorded as an AE on the CRF and reported as a non-serious Event of Clinical Interest (ECI), using the terminology “accidental or intentional overdose without adverse effect.”

All reports of overdose either SAE or ECI must be reported within 24hrs of the PI or designee becoming aware of the event to the RM-CTU by [contact] or e-mail to [contact] who will inform MSD.

7.8 Definition of a Serious Adverse Reaction (SAR)

A SAR is defined as an SAE that is judged to be related to any dose of study drug administered to the patient.

7.9 Definition of Suspected, Unexpected, Serious, Adverse Reactions (SUSARs)

A SUSAR is a serious adverse reaction, the nature or severity of which is not consistent with the applicable product information (e.g. investigator's brochure for an unauthorised investigational product or summary of product characteristics for an authorised product). The Reference Safety Information for the PEACH trial is

contained in the Investigator's Brochure. The Investigator's Brochure will be used for assessing the expectedness of all adverse reactions.

7.10 Reporting of SUSARs

All SUSARs must be reported using the SAE report form within 24hrs of the PI/designee becoming aware of the event to the RM-CTU by [contact] or e-mail to [contact]. The RM-CTU will in turn notify the Sponsor, MSD, relevant Independent Ethics Committee (IEC) / Institutional review, appropriate regulatory authorities and the participating Principal Investigators in accordance with regulatory requirements and within the timelines as defined below:

- For fatal and life-threatening SUSARs the sponsor should report at least the minimum information as soon as possible and in any case no later than seven days after being made aware of the case.
- SUSARs which are not fatal and not life-threatening are to be reported within 15 days.

Follow up of patients who have experienced a SUSAR should continue until recovery is complete or the condition has stabilised.

7.11 Annual Reporting of Serious Adverse Events

The Development Safety Update Report (DSUR) will be submitted annually on the anniversary of regulatory approval for the trial. This report will be submitted to regulatory authorities and Independent Ethics Committees (IEC) in accordance with all applicable global laws and regulations. Copies will be forwarded to the Sponsor, MSD and Investigators.

7.12 Urgent safety measures

The Sponsor or Investigator may take appropriate urgent safety measures (USMs) in order to protect the patient of a clinical trial against any immediate hazard to their health or safety. This includes procedures taken to protect patients from pandemics or infections that pose serious risk to human health.

USMs may be taken without prior notification from the competent authority. The CI / DI must notify the Medicines and Healthcare Products Regulations (MHRA), Research Ethics Committee (REC) and Sponsor immediately and in any event, within 3 days of the measures taken and the plan for further action. The initial notification to the MHRA will be by telephone, and then a written notice will be sent out within 3 days. Should the site initiate a USM, the Investigator must inform the RM-CTU immediately either by:

- Email: [contact]
- [contact]
- [contact]

The notification must include:

- the date of the USM;
- who took the decision; and
- why action was taken.

RM-CTU will then inform the Sponsor who will notify the MHRA and the REC within three days of USM initiation. RM-CTU will distribute the response and any subsequent amendments to the trial sites.

CI Contact Details:

Name: [name]
Address: The Royal Marsden NHS Foundation Trust
[name]
[name]
Email: [contact]

8.0 STATISTICAL ANALYSIS PLAN

8.1 Statistical Analysis Plan Summary

8.2 Endpoints

8.2.1 Primary Endpoint

A: To establish the maximum tolerated dose that can safely be combined with platin-based chemoradiotherapy in patients with HPV-ve and with HPV+ve LA-SCCHN, respectively.

B: To evaluate acute toxicity in each HPV group as measured during treatment by CTCAE v4.0.

8.2.2 Secondary Endpoints

1. To measure the PFS and overall survival at 6 months, 1 year and 2 years, respectively.
2. To measure the duration of clinical benefit using RECIST at 6 months, 1 year and 2 years, respectively.
3. To evaluate late radiotherapy toxicities as measured during treatment by LENT SOMA 52 weeks from the end of radiation therapy (week 7).

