3.5.2 Post-Treatment Follow-up (A) Visit – Patients who complete all cycles of pembrolizumab

Patients who complete all cycles of pembrolizumab without disease progression or suffering unacceptable toxicities will be seen at 4 weeks and 8 weeks after the last dose of pembrolizumab. Procedures and assessments will be performed as defined in the schedule of study assessment (Table 2).

3.5.3 Post-Treatment Follow-up (B) Visit – Patients who discontinue without progression.

Patients who discontinue pembrolizumab for any reason other than disease progression will be seen 8 weeks after the last dose of pembrolizumab. Procedures and assessments will be performed as defined in the schedule of study assessment (Table 2).

3.5.4 12 Weeks Safety Follow-up (SFU) Visit

In addition to the above follow up all patients are expected to attend a mandatory safety follow-up visit conducted at 12 weeks after the last dose of pembrolizumab or before the initiation of a new anti-cancer treatment, whichever comes first. All AEs that occur prior to the safety follow-up visit should be recorded as described in section 7.0. After the safety follow-up any unresolved AEs at the patient's last visit should be followed up for as long as medically indicated, but without further recording in the CRF.

3.5.5 Post-Safety Follow-up (A) Visits – Patients who complete all cycles of pembrolizumab.

Patients who complete all cycles of pembrolizumab without disease progression or suffering unacceptable toxicities will move into the post-safety follow-up (A) phase. These patients will be assessed every 4 weeks from SFU for 9 months or until the patient suffers disease progression, they begin a new anti-cancer treatment or they withdraw. Each follow up visit will monitor disease status and assess for any new anti-cancer therapies. If a patient progresses or begins a new anti-cancer therapy they will move to the survival follow-up phase.

3.5.6 Post-Safety Follow-up (B) Visits – Patients who discontinue without progression.

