Patients who discontinue pembrolizumab for any reason other than disease progression will move into the post-safety follow-up (B) phase. These patients will be assessed every 8 weeks from SFU for 9 months or until the patient suffers disease progression, they begin a new anti-cancer treatment or they withdraw. Each follow-up visits will monitor disease status and assess for any new anti-cancer therapies initiated. If a patient progresses or begins a new anti-cancer therapy they will move to the survival follow-up phase.

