3.5.7 Survival Follow-up – Patients who have disease progression

Once a patient experiences confirmed disease progression or starts a new anti-cancer therapy, the patient moves into the survival follow-up phase and should be contacted by telephone every 12 weeks to assess for survival status until death, withdrawal of consent, or the end of the study, whichever occurs first. If a patient progresses on treatment they will also be required to attend a SFU at 12 weeks or before the initiation of a new anti-cancer treatment; whichever comes first.

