3.6 Study Termination

The end of the study is defined when the last patient has completed post-safety follow-up phase (A)/(B) or discontinued the study for other reasons.

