Trial Period:		Screening Phase	Treatment Cycles – Every 3 Weeks												End of Treatment - At time of discontinuation of treatment ⁴	Post-Treatment							
Treatment Cycle/Week Title:			Pre-Loading Dose	C 1	C 2	C 3	C 3	C 3	C 4	C 4	C 4	C 5	C 6	C 7		Post-Treatment Follow-up (A) ¹	Post-Treatment Follow-up (B) ²	Safety Follow-up (SFU)	Post-Safety Follow-up (A) ¹	Post-Safety Follow-up (B) ²	Survival Follow-up		
Scheduling Window (Days):				Wk 0	Wk 3	Wk 6	Wk 7 ⁸	Wk 8	Wk 9	Wk 10	Wk 11	Wk 12	Wk 15	Wk 18		4 wks and 8 wks from last dose of Pembrolizumab	8 wks from last dose of Pembrolizumab	12 wks from last dose of Pembrolizumab ³	Every 4 wks from SFU for 9 months	Every 8 wks from SFU for 9 months	Every 12 wks from progression / initiation of anti-cancer treatment		
Administrative Procedures																							
Informed Consent	X																						
Inclusion/Exclusion Criteria	X																						
Demographics, Medical & Treatment History, Smoking Status	X																						
Anti-cancer therapy Review																X	X	X	X	X			
Survival / Disease Status																X	X	X	X	X	X		
Clinical Procedures / Assessments																							
Review Adverse Events		X	X	X	X	X		X	X	X	X	X	X	X	X	X	X	X	X				
Radiation Toxicity Review				X	X			X	X	X	X	X	X	X	X	X	X	X	X	X			
Prior and Concomitant Medication Review	X	X	X	X	X			X	X	X	X	X	X	X	X	X	X	X	X				
Full Physical Exam	X																						
Directed Physical Exam		X	X	X	X	X		X	X	X	X	X	X	X	X	X			X				
Vital Signs, Weight & ECOG	X	X	X	X	X			X	X	X	X	X	X	X	X				X				
Height	X																						
Pregnancy Test – Urine/Serum	X																						
T3, T4, TSH, PT and aPTT	X			X		X			X		X		X						X				
Haematology & Biochemistry	X	X	X	X	X			X	X	X	X	X	X	X	X				X				
Urinalysis	X																						
Admin of Pembrolizumab		X	X	X	X				X			X	X	X									
Admin of Radiotherapy			X	X	X	X																	
Admin of Chemotherapy			X	X	X																		
Tumour Imaging	X													X ⁷									
Clinical disease assessment	X		X	X	X			X			X	X											
Archival collection or new tumour biopsy	X		X ⁵	X ⁵																			
HPV testing (p16 Immunohistochemistry)	X																						
Research Blood Collection (OPTIONAL)	X			X				X			X				X ⁶								
Neck dissection																							

1. For patients who have completed 8 doses of pembrolizumab and have not progressed or discontinued from unacceptable toxicities.

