8.2.6 Timing of analysis

For the primary end point, the results of each dosing level will be reviewed by the safety review committee (SRC) before recruitment to the next dose level can begin and once the MTD has been determined the trial enters the expansion cohort. Analysis of the secondary endpoints will take place 1 year after the enrolment of the last patient. Analysis of the exploratory endpoints will be reported once all the relevant samples have been collected and analysed.

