9.8 End of Trial

The end of the trial is defined as the last patient's last visit.

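### Two-year PFS, OS and clinical benefit are promised, but scheduled follow-up of progression-free patients ends at about 16 months or earlier, and the secondary analysis is set 1 year after last enrolment

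*Combined protocol and SAP*

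**What the plan says.** **Landmarks.** Section 8.2.2 gives the endpoint as "To measure the PFS and overall survival at 6 months, 1 year and 2 years, respectively"; the Trial Summary and 2.2.2 say the same. Duration of clinical benefit has the same three landmarks. Section 8.2.5 commits to Kaplan-Meier rates at all three and censors event-free patients on the last date they are known to be alive.

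**Visits.** The safety follow-up visit (SFU) is 12 weeks after the last dose (3.5.4). For completers, 3.5.5 says "These patients will be assessed every 4 weeks from SFU for 9 months". For patients who stop early without progression, 3.5.6 says "These patients will be assessed every 8 weeks from SFU for 9 months".

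**Survival calls.** Section 3.5.7: "Once a patient experiences confirmed disease progression or starts a new anti-cancer therapy, the patient moves into the survival follow-up phase". Table 2 times these calls "Every 12 wks from progression / initiation of anti-cancer treatment". They stop at the end of the study, which 3.6 ties to the last patient finishing post-safety follow-up and 9.8 to that patient's final visit.

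**Imaging.** The Trial Summary, Table 2 footnote 7 and one sentence of 5.3.9.3 plan a scan at cycle 6, then 12-weekly scans over the following 12 months. A later sentence of 5.3.9.3 has scanning go on until progression, new treatment, withdrawal, death or the end of the study.

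**Analysis date.** Section 8.2.6: "Analysis of the secondary endpoints will take place 1 year after the enrolment of the last patient".

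**Durations.** The Trial Summary states 15-18 months of participation and 30 months for the trial.

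**The concern.** The 2-year landmarks need information at 24 months on patients who have not yet had the event. The visit schedule, the survival calls and the analysis date all appear to stop short of that for progression-free patients.

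The effect differs by endpoint. For PFS and clinical benefit, the patients who determine the 2-year figure are no longer being assessed. For OS, contact continues in one prognostic group only: those who have progressed or changed therapy. A 2-year OS from that risk set is not merely immature, because the censoring depends on prognosis. The trial is meant to give an indication of activity (1.2.3) and to precede a randomised phase 2 study (3.1), so a misleading 2-year figure could be carried forward.

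**Working it through.** **Conventions.** 1 month = 365.25/12/7 = 4.348 weeks, so 9 months = 39.1 weeks. Cycle 1 is week 0 and the pre-loading dose is week -2 (3.2). Time runs from the pre-loading dose, taken as the start of treatment in 8.2.5. No treatment delays.

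**1. Leaving scheduled follow-up.** Exit week = week of last dose + 12 + 39.1; months = (exit week + 2)/4.348.

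| Last dose | Week | Exit week | Months from pre-loading dose |
|---|---|---|---|
| Pre-loading dose only | -2 | 49.1 | 11.8 |
| Cycle 3 | 6 | 57.1 | 13.6 |
| Cycle 6 | 15 | 66.1 | 15.7 |
| Cycle 7 (completer) | 18 | 69.1 | 16.4 |

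The completer figure reproduces the stated 15-18 months of participation (17.3 months if 28 days of screening are added). Twenty-four months is week 24 x 4.348 - 2 = 102.4. The gap for a completer is 24 - 16.4 = 7.6 months, about 33 weeks. One 12-week interval between doses instead of 3 weeks adds 9 weeks and moves exit only to about 18.4 months.

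**2. Imaging on the 12-month reading.** Scans fall at weeks 15, 27, 39, 51 and 63. The window closes at 15 + 52.2 = week 67.2, before the next slot at week 75. The last scan is at (63 + 2)/4.348 = about 14.9 months.

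**3. Imaging on the open-ended reading.** The study ends about 16.4 months after the last patient starts. A patient is imaged to 24 months only if enrolled at least 24 - 16.4 = 7.6 months before the last one.

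**4. Direction of the OS error.** Let e be the time of exit, S(e) the OS at e, p the share of survivors at e who are progression-free, and s0 and s1 the probabilities of surviving from e to 24 months for progression-free and for progressed or re-treated survivors.

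- True OS(24) = S(e) x [p s0 + (1 - p) s1]
- Kaplan-Meier OS(24) = S(e) x s1, because only the second group stays at risk
- Shortfall = S(e) x p x (s0 - s1)

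The shortfall is positive whenever progressed patients die faster (s1 < s0). The same applies at each earlier exit of a patient who stopped treatment. The documents give none of p, s0 or s1, so there is a direction but no size.

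**5. Calendar time at the planned analysis.** Implied accrual, if the 30 months include full follow-up of the last patient, is 30 - 16.4 = 13.6 months. Under uniform accrual over A months (assumption), the share with 24 months since entry is (A - 12)/A.

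- A = 13.6: 1.6/13.6 = 12%, about 4 of 36
- A = 18: 33%, 12 of 36
- A = 24: 50%, 18 of 36

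The last two exceed the stated duration (18 + 16.4 = 34.4 months) and are shown only as a range. Accrual will not be uniform. The dose-limiting toxicity window runs to week 13, or 15 weeks from the pre-loading dose (3.3), and the longest escalation path has four such waits per HPV cohort: 60 weeks, or 13.8 months, before expansion. The counts are therefore indicative.

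**6. Late toxicity.** The 52-week LENT SOMA point is week 7 + 52 = 59. The analysis date for the last patient is about 52.2 - 2 = week 50.2, taking enrolment as the pre-loading dose. It comes first by about 9 weeks, roughly 2 months.

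**The case against.** **Imaging may be open-ended.** On the later sentence of 5.3.9.3, early enrollees could be scanned past 24 months. With 13.6 months of uniform accrual, those enrolled in the first 13.6 - 7.6 = 6.0 months qualify by the end of the study: 6.0/13.6 = 44%, about 16 of 36. This stands to the extent that a reader should not infer that no progression-free patient could ever be assessed at 2 years. It does not rescue the plan. The sentence conflicts with the 12-month limit in the same section and in Table 2, it cannot reach 24 months for later enrollees, and it adds no survival contact.

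**Kaplan-Meier does not need 24 months on everyone.** True. Staggered entry alone is ordinary administrative censoring, and 10.11 allows reporting from final listings at the end of the trial. The early analysis date by itself costs precision. The defect is that contact after exit depends on having progressed or changed therapy.

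**Vital status could come from hospital records.** No section plans this. For PFS it would do harm: 8.2.5 censors at the last date known alive, so unassessed time would count as progression-free.

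**Section 6.10 mentions 24 months of treatment.** That does not match the eight-dose regimen and adds no follow-up.

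**A reader might put a number on the OS bias.** That needs post-progression survival and the share of survivors who are progression-free. The documents give neither, so only the direction is supportable.

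**These are descriptive secondary endpoints in a phase I trial of 6 to 36 patients.** Agreed, and this limits the severity.

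**Conclusion.** The 2-year landmarks are not supported by the stated schedule and should be changed. Scheduled follow-up of progression-free patients ends at about 16.4 months for completers and 11.8-15.7 months for early stoppers, assuming no delays. On the 12-month imaging reading they have no planned disease assessment at 24 months. OS beyond these exits is informatively censored, and biased downward if progressed or re-treated patients die faster; the size is not determinable. About 12% of patients would have 24 calendar months by the planned analysis, given 13.6 months of uniform accrual.

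The point goes no further. A reader might infer that the trial's main conclusion is at risk, but the primary endpoint, the dose decision and the 6-month landmark are unaffected. Completers pass 12 months. Patients who stop at or before cycle 2 without progression have their last 8-weekly visit (32 weeks after the SFU) at 10.1-11.3 months, which numbers at risk would show. The late-toxicity data are not lost: they miss the planned analysis for the last patients but can be reported later under 10.11.

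**What to change.** Choose one.

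**(a) Drop the 2-year landmark** from the Trial Summary, 2.2.2, 8.2.2 and 8.2.5. Report PFS, OS and clinical benefit at 6 and 12 months with numbers at risk. State that curves are not interpreted beyond scheduled follow-up: about 16 months for completers, earlier where early stoppers have left. Move the secondary analysis in 8.2.6 to when the last patient completes post-safety follow-up, about week 69. That also passes the week-59 LENT SOMA point; patients whose last dose was cycle 3 or earlier leave by week 57, so report how many were assessed. Cost: wording, and an analysis 16.4 - 12 = 4.4 months later.

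**(b) Keep 2-year OS only.** Extend the 12-weekly telephone contact to every patient until that patient's own 24 months, and move the end of study (3.6, 9.8) and the analysis (8.2.6) to when the last patient reaches 24 months. Drop 2-year PFS and clinical benefit unless disease status is also collected. Cost: (102.4 - exit week)/12 calls per progression-free patient, rounded up. This is 3 for a completer, 4 after cycle 3 and 5 after the pre-loading dose only, for at most 36 patients. Further calls to progressed patients come on top, because the study ends about 7.6 months later. The analysis is about 12 months later than now.

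In either case, reconcile the two imaging sentences in 5.3.9.3 with each other and with Table 2 footnote 7.

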8.2.3 Exploratory Endpoints

A. Peripheral blood analysis

1. PBMC biomarkers of immune response: Quantitative assays of CD4, CD8, T regulatory cell (CD4/CD25, FOXP3), B cells and NK cells will be performed. In addition, where feasible, functional assays of cytokine release will be performed.
2. Analysis of circulating free tumour DNA – pre, per- and post-treatment.

B. Tumour Biopsy samples

1. Immunohistochemical analysis to identify immune infiltrates (T cells [CD4⁺, CD8⁺, CD4⁺/CD25⁺ Treg], B cells, macrophages, NK cells), levels of expression of PD1 (and other immune exhaustion markers) on immune cells, levels of PDL1 expression on tumour cells.

8.2.4 Sample Size

With a minimum of 3 patients in each HPV cohort at dose level 1, a minimum of 6 patients are required. With a maximum of 6 patients in each of the 2 dose levels and a further 6 in the expansion phase, a maximum of 18 patients are required in each HPV cohort, respectively. This gives a minimum of 6 to a maximum of 36 patients, respectively, are required for the trial.

8.2.5 Data analysis

All quantitative data will be presented as number of observations, means and SDs for normally distributed data or as median and interquartile ranges for data that appear to be non-normally distributed. Qualitative data will be presented as number of observations and frequencies. When appropriate, data will be presented together with 95% confidence intervals. All statistical tests will be two-tailed and a p-value <0.05 (5%) will be considered as achieving statistical significance. The analysis will be performed separately in HPV-ve and HPV+ve cohorts, respectively.

- Baseline characteristics will be summarized using descriptive statistics. Dose limiting toxicity will be summarized using overall frequencies. Incidence (highest grade) of side effects of radiotherapy (CTCAE scale v 4.0, for acute side effects and LENT SOMA for late radiotherapy scoring systems) will be reported.
- Duration of clinical benefit will be calculated as the number of patients who had a best overall response of CR, PR, or SD according to the RECIST criteria until the first date of recurrence or progressive disease (PD) and will be measured at the landmark points in the study **6 months, 1 year and 2 years, respectively**. They will be presented as proportions and 95% confidence intervals will be reported if appropriate.
- Progression free and overall survival will be determined using Kaplan-Meier methods **presenting the median survival times, and survival rates will be reported at 6 months, 1 and 2 years, respectively**. Overall survival will be measured from date of treatment to date of death from any cause; surviving patients will be censored at date last known to be alive. Progression free survival will be measured from start of treatment to date of first appearance of disease progression, relapse or death from any cause. Patients alive without progression or relapse will be censored at date last known to be alive. Survival curves will be estimated for each HPV cohort and compared using the log-rank test.

- The levels of CD4, CD8, T regulatory cell (CD4/CD25, FOXP3), B cells, NK cells and Circulating free tumour DNA pre RT, during RT and post RT will be presented as descriptive statistics according to their HPV status. The expression of PD1 (and other immune exhaustion markers) on immune cells and PDL1 on tumour cells will be presented as descriptive statistics.

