1.2.3.1 Efficacy Endpoints

Acute and late toxicity assessed by CTCAEv4 will be used to judge the tolerability of a combination of pembrolizumab and chemoradiotherapy to ensure that the treatment does not cause excess toxicity.

Flexible nasendoscopy and standard ENT examination will be performed to support the measurement the clinical response of disease. These findings will be augmented by imaging investigations performed according to the schedule of study assessment (in Section 5.0).

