2.2.2 Secondary Endpoints

1. To measure the PFS and overall survival at 6 months, 1 year and 2 years.
2. To measure the duration of clinical benefit using RECIST at 6 months, 1 year and 2 years.
3. To evaluate late radiotherapy toxicities as measured during treatment by LENT SOMA 52 weeks from the end of radiation therapy (week 7).

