5.3.2 Radiation Toxicity Assessment

Radiotherapy toxicity will be documented using the LENT SOMA radiation toxicity grading system (Appendix 3). Assessments will take place at each visit as defined by the study's schedule of assessment (Table 2)

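### The late-toxicity endpoint is timed both during treatment and at 52 weeks after radiotherapy, and section 8.2.5 reports the highest LENT SOMA grade with no late window and no pre-radiotherapy score

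*Combined protocol and SAP*

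**What the plan says.** - **Endpoint.** Section 8.2.2 lists as the third secondary endpoint: "To evaluate late radiotherapy toxicities as measured during treatment by LENT SOMA 52 weeks from the end of radiation therapy (week 7". Section 2.2.2 has the same wording.
- **Analysis.** Section 8.2.5 reports "Incidence (highest grade) of side effects of radiotherapy (CTCAE scale v 4.0, for acute side effects and LENT SOMA for late radiotherapy scoring systems". That sentence gives no start, end or visit for the late grade, and no baseline adjustment.
- **Collection.** Section 5.3.2 states: "Radiotherapy toxicity will be documented using the LENT SOMA radiation toxicity grading system". On timing it adds: "Assessments will take place at each visit as defined by the study's schedule of assessment (Table 2". Table 2 marks the radiation toxicity review first at week 3, then at week 6, at the visits after chemoradiotherapy, and through both post-safety follow-up routes. It has no mark at screening, pre-loading or week 0.
- **A second instrument.** Section 1.2.3.1 states: "Acute and late toxicity assessed by CTCAEv4 will be used to judge the tolerability". Under 5.3.1, CTCAE events are recorded only up to the safety visit 12 weeks after the last pembrolizumab dose.
- **Follow-up after early stopping.** For patients who stop pembrolizumab without progression, section 3.5.6 states: "These patients will be assessed every 8 weeks from SFU for 9 months".
- **Analysis date.** Section 8.2.6 places the secondary analysis one year after the last patient is enrolled.

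**The concern.** Endpoint 3 cannot be applied as written. Week 59 lies well after radiotherapy (ends week 7) and after the last pembrolizumab dose (week 18), so a measurement during treatment cannot also be the 52-week measurement. The sentence also leaves open whether the grade is taken at 52 weeks or at any time up to then.

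Section 8.2.5 does not settle this. It drops the 52-week anchor and labels everything scored on LENT SOMA as late. A highest grade can only rise as visits are added, so a single transient high score at week 3 or 6 would fix a patient's late grade even if it had resolved by week 59.

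Section 1.2.3 says the study aims to show whether late toxicity is acceptable, and section 3.1 says the dose goes forward to a randomised phase 2 trial. With at most 18 patients per HPV cohort, a few misclassified patients would visibly change the reported rate. A pre-radiotherapy score that was never taken cannot be recovered later.

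**Working it through.** The plan gives no figure for this endpoint to reproduce, so the check maps the visits to weeks.

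**1. The anchor.** Radiotherapy starts at week 0 and runs 7 weeks (Trial Summary). 7 + 52 = week 59.

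**2. LENT SOMA reviews for a completer.**
- Table 2: weeks 3, 6, 8, 9, 10, 11, 12, 15, 18 (9 reviews). The extracted table slips by one column after week 7. The pembrolizumab row slips in the same way and confirms the alignment.
- 4, 8 and 12 weeks after the last dose at week 18: weeks 22, 26, 30 (3 reviews).
- Every 4 weeks for 9 months (9 × 52/12 = 39 weeks) from week 30: weeks 34, 38, 42, 46, 50, 54, 58, 62, 66 (9 reviews).
- Total: 9 + 3 + 9 = 21.

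**3. How many are not late.**
- During radiotherapy: weeks 3 and 6, so 2 of 21.
- Within the plan's DLT window, 6 weeks after chemoradiotherapy (7 + 6 = week 13): 7 of 21.
- Before an assumed 90-day cut, which is not in the documents (7 + 90/7 ≈ week 20): 9 of 21, leaving 12 after it.

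**4. What a highest-ever grade could do (illustration only).** Take a true late grade 3 rate of 15–30%, the dysphagia range in section 1.2.1, and assume an on-treatment rate of 20–60%.
- Independent: 1 − (1 − 0.15)(1 − 0.20) = 32%, up to 1 − (1 − 0.30)(1 − 0.60) = 72%.
- Full overlap: the larger of the two rates, 20% to 60%. There is no inflation where the late rate is already the larger (30% against 20%).
- In 18 patients: 3.6 to 13.0 counted, against 2.7 to 5.4 truly late.

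**5. CTCAE as the late instrument.** For a completer, recording ends at 18 + 12 = week 30, which is 30 − 7 = 23 weeks after radiotherapy. It cannot give a 52-week result.

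**6. Follow-up of early stoppers without progression.** The nine-month limit is last dose + 12 + 39 weeks. The last eight-weekly visit inside it is last dose + 12 + 32 weeks.

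| Last dose (week) | Nine-month limit (week) | Last visit inside it (week) |
|---|---|---|
| −2 (pre-load) | 49 | 42 |
| 0 | 51 | 44 |
| 3 | 54 | 47 |
| 6 | 57 | 50 |
| 9 | 60 | 53 |
| 12 | 63 | 56 |
| 15 | 66 | 59 |

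On the nine-month limit, a last dose at or before week 6 ends follow-up before week 59. Counting only visits inside the limit, a last dose at week 9 or 12 also falls short.

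**7. Analysis date.** If enrolment is close to the pre-loading dose (week −2), one year later is −2 + 52 = week 50 for the last patient. That is 50 − 7 = 43 weeks after radiotherapy and 9 weeks before week 59. An earlier enrolment date, such as consent, widens the gap.

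**The case against.** The strongest reply is that a late anchor does exist: both 2.2.2 and 8.2.2 specify "LENT SOMA 52 weeks from the end of radiation therapy (week 7". Section 8.2.5 also assigns LENT SOMA to late effects, so its highest grade can be read as the highest late grade. This stands to the extent that mixing acute and late grades is a risk under a literal reading, not something the plan states. It does not remove the risk, because the anchor shares a sentence with a contradictory phrase and is absent from the analysis rule.

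A reader might infer that the late-toxicity table would mostly repeat acute toxicity. The documents do not show that. Twelve of a completer's 21 reviews fall after week 20, the LENT SOMA scale is only cited, and no section gives the timing of peak reactions.

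A reader might also infer that the 52-week score is missing for everyone who stopped because of toxicity. That is too broad. On the nine-month limit only a last dose at or before week 6 falls short, and a week-6 stop ends at week 57, inside a ±4-week tolerance. The number of such patients is unknown.

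Baseline status is not wholly undocumented. Screening includes medical history, a full examination and a clinical disease assessment, and adverse events are recorded from the pre-loading dose, two weeks before radiotherapy. None of this is on the LENT SOMA scale, so the gap remains but is narrower than it looks.

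The CTCAE statement sits in the rationale, and the operative sections name LENT SOMA. It is a secondary inconsistency.

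Finally, this is a descriptive secondary endpoint that the Trial Summary's endpoint list omits, and visit-level scores will be held, so a window can still be set before analysis. That lowers the severity. It does not help with the missing baseline score.

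**Conclusion.** The point holds, at moderate severity. Endpoint 3 contradicts itself, and 8.2.5 does not carry the 52-week anchor into a highest-grade summary of scores that begin during radiotherapy. Followed literally, it lets 7 of a completer's 21 reviews (the plan's own DLT window), or 9 of 21 (an assumed 90-day cut), set the late grade. No LENT SOMA score before radiotherapy identifies existing deficits. Week 59 is also out of reach for non-progressing patients whose last dose is at or before week 6 (nine-month limit), and for the last patient at the analysis date if enrolment is close to pre-loading.

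The inflation figures in step 4 rest on an assumed on-treatment rate and show direction only. A reader might infer that the dose decision is affected. It is not, because the DLT definition and escalation rules (3.3, 12.1.4) do not use LENT SOMA.

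**What to change.** - **2.2.2 and 8.2.2:** remove the during-treatment phrase from endpoint 3.
- **8.2.5:** report the highest LENT SOMA grade only within a stated late window, for example from 90 days after radiotherapy to the week-59 assessment. The 90-day cut is an assumption for the sponsor to confirm. Also report the grade at about week 59 (±4 weeks), and tabulate earlier LENT SOMA scores separately. Let the window include the ±4-week tolerance, so that a week-62 visit used as the 52-week score is not excluded.
- **Table 2 and 5.3.2:** add one LENT SOMA score at the existing screening or week 0 visit.
- **1.2.3.1:** name LENT SOMA for late toxicity.
- **8.2.6:** run the late-toxicity analysis after the last patient's week-59 assessment, and report how many patients lack a week-59 score because scheduled follow-up ended earlier.

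The cost is wording changes, one extra score at a visit that already takes place, and an analysis about 9 weeks later for the last patient. Fewer scores enter the late summary: for a completer, 10 of 21 reviews fall between weeks 20 and 59 (weeks 22, 26, 30, 34, 38, 42, 46, 50, 54 and 58), or 11 if the tolerance admits week 62.
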